6.4.2 Control (“Sham”) Treatment in the Control Group

As described in Section 3.2.2, no inert placebo exists. The optimal control, therefore, is to simulate study drug treatment in a masked fashion by bringing the ADS to the bedside but not administering any study drug, a procedure known as “sham” treatment.

For sham treatment, no active drug will be prepared. Instead, the ADS will be prepared and delivered to the bedside in a masked manner. Masking will occur as with active treatment (eg, behind a curtain). The subject will be connected to the same setup as active subjects (using the study nCPAP and study airway connector; see Section 8.7.3). Following completion of the setup, subjects will need to stabilize for at least 15 minutes. Subjects receiving sham will simulate being connected to nCPAP via the ADS but the ADS itself will not be powered on or connected. The start time for sham treatment (treatment initiation) will be the time at which this simulated connection occurs; the stop time will be 110 minutes later (to account for an approximate 10 minutes to switch the syringe and cartridge in the active treatment group). The subject will remain masked for the same duration as active subjects. As with the active treatment, if the subject’s FiO₂ level is not at room air (0.21) by the end of the “treatment” time, the site should prepare and conduct a repeat “treatment”; each repeat treatment time will be 50 minutes. At the end of the assigned sham treatment time, the subject will be switched to clean nCPAP equipment (if necessary), as occurs at the end of active treatment. Masking equipment may then be removed.

As with active treatment, control/sham treatment is to begin within 2 hours after randomization. Repeat control/sham treatments (up to 3) are to be given if repeat treatment criteria are met, unless it is unsafe to do so in the judgment of the investigator (see Section 6.6). As described in Section 3.2.2, repeat treatment with control/sham in subjects who do not require intubation is ethical.

6.5 Treatment Groups and Method of Treatment Group Assignment

Subjects will be assigned to receive either 160 mg TPL/kg lucinactant for inhalation in conjunction with nCPAP or control (sham treatment).

Table 6-2. Study Assignments by Treatment Groups

Treatment Group	Study Assignment
160 mg/kg	160 mg TPL/kg of lucinactant for inhalation, delivered as two consecutive 50-minute administrations, in conjunction with nCPAP (n ≈ 65) Up to 3 repeat study treatments of lucinactant for inhalation 80 mg TPL/kg are to be given if repeat treatment criteria are met
Control	Continuous nCPAP with sham drug treatment for 110 minutes (n ≈ 65) Up to 3 repeats of 50-minute sham treatments are to be given if repeat treatment criteria are met.

Note: The first 2 subjects at each site will receive open-label active treatment. Masking procedures for the initial treatment will be followed for all repeat treatments in all treatment groups

Preterm neonates who successfully meet all eligibility criteria will be randomly assigned within their applicable stratum (26 to 28 completed weeks PMA or 29 to 32 completed weeks PMA) to one of the 2 treatment groups in a 1:1 ratio. Subjects will be randomized/enrolled using centralized allocation electronically (eg, interactive response technology [IRT]), including the open-label subjects (the first 2 subjects at each site). Neonates from multiple births will be randomized independently. Randomization information will be provided to the study drug preparer (eg, pharmacist). The PI, study staff (eg, site coordinator) (as applicable), and attending physicians as appropriate will be masked to the treatment assignment, as described in the site's blinding/masking plan. Infants who are randomized and on study nCPAP but no longer meet qualification criteria before treatment will still receive the study treatment, unless it is unsafe to do so in the opinion of the investigator.

6.6 Repeat Treatments

Up to 3 repeat treatments will be administered to each subject, regardless of treatment group assignment, up to 36 hours following randomization. For each subject, repeat treatments will occur if repeat treatment criteria are met, unless it is unsafe to do so in the judgment of the investigator. It is required that all subjects receive a repeat treatment after the previous treatment, unless the subject is on an FiO₂ of 0.21 (room air). Masking procedures used for the initial treatment will be followed for repeat treatments (see Section 6.7).

The repeat treatment criteria are defined as follows:

- Time: \geq 20 minutes from completion of the previous treatment (up to 36 hours following randomization)
- Respiratory support: Subject has a need for $\text{FiO}_2 > 0.21$ to maintain SpO_2 of 90% to 95%.

The repeat treatment should occur as soon as possible after the 20-minute time period has elapsed, but no more than 1 hour after meeting criteria.

As with the initial treatment, the randomization/inventory system will be used to receive the drug kit assignments, and all other procedures that were performed for the initial treatment will be followed for the administration of the repeat treatments.

6.7 Study Masking

In order to minimize bias in subject assessments, study treatment masking (blinding) will be employed. Details of the masking procedure are provided in the 03-CL-1702 Overall Blinding Plan, Blinding Procedure, Blinding Maintenance and Assurance Plan, and Statistical Analysis Plan documents. The blinding plan is outlined as follows:

- a. In all circumstances, subject safety takes precedence over maintenance of study masking. If at any point masking equipment interferes with emergent patient care or knowledge of study treatment is required for patient management, then the blind should be broken. If this occurs, Windtree must be notified as soon as possible (see Section 9.3.2).
- b. Personnel making or influencing clinical decisions – especially regarding intubation or the level of respiratory support – must be masked from treatment assignment. Every effort should be made to maintain study masking at all times unless the blind needs to be broken for reasons of subject safety. Clinicians may be masked for different subjects at different times, depending on the logistics at each site.
- c. As there are potentially many ways in which treatment assignment might be masked, each site will create a site-specific blinding plan to be followed throughout the study that specifies which staff members (or types of staff members) are masked and which are not, and at what times. This blinding plan must be approved by Windtree prior to subject recruitment.
- d. Operational requirements of blinding are described in the Blinding Procedure document. Generally, active or sham drug syringes and materials will be prepared by an unmasked drug preparer at the time dosing is required and will be obscured from view when

transported to the bedside with the ADS. Once at the bedside, visual barriers will be put in place to block dosing equipment from view outside the immediate bedside area. An unmasked dosing team will then administer active study drug or sham drug treatment. The start time (treatment initiation) for sham will be the time at which the sham setup is complete and the nCPAP circuit is interrupted (to simulate connection to the ADS); the stop time will be 110 minutes later for the initial treatment.

- e. As the ADS is virtually silent, no auditory blinding devices are required (eg, “white-noise” generator). At the conclusion of treatment, unless a repeat treatment is immediately warranted, the dosing team will replace any visibly soiled nCPAP equipment, break down the dosing equipment, remove all residual active drug from the subject, remove the visual barriers, and transport the waste (obscured from view) for disposal, and the ADS back to storage.

6.8 Early Discontinuation of Study Treatment

The administration of study treatment may be discontinued at any time prior to the completion of dosing if certain device error codes occur which cannot be corrected in a safe and timely manner or based on the clinical judgment of the PI. Reasons for discontinuation of study treatment include, but are not limited to the following:

1. Device failure or malfunction occurs. If device failure or malfunction occurs, the user should follow the on-screen instructions to resolve the issue. If they are unable to resolve the issue, they must contact the previously-identified Windtree representative for further instructions (Section 9.2).
2. Automatic treatment interruption due to a pre-defined condition (eg, syringe high pressure error). If automatic shutdown occurs, Windtree personnel should be contacted as soon as possible (per Section 9.2).
3. An AE or ADE which places subject safety at risk (eg, pulmonary hemorrhage, airway obstruction).
4. If, in the PI’s best medical judgment, continuing the subject’s exposure to study treatment is not in the best interest of the subject’s safety.

5. Signs of acute respiratory deterioration develop, as evidenced by a clinically significant increase in respiratory rate or effort (work of breathing) plus at least one of the following:
 - a. A persistent (at least 10 minutes) $\text{FiO}_2 \geq 0.70$ or a sustained increase from baseline by ≥ 0.30 to maintain SpO_2 90% to 95%
 - b. A persistent (at least 5 minutes) transcutaneous $\text{PCO}_2 > 70$ mm Hg or an increase from baseline by ≥ 20 mm Hg
 - c. Recurring episodes of bradycardia
 - d. A sustained apneic event (≥ 20 seconds)

Subjects whose treatment is discontinued based on the PI's judgment will continue in the study. Subjects whose treatment is discontinued based on the parent/guardian's withdrawal of consent must be withdrawn from the study and no further data collection will be done.

In accordance with local institutional practices, an approved SRT must be made available to subjects demonstrating a clinical need if dosing is discontinued early.

6.9 Clinical Study Supplies at the Clinical Study Site

6.9.1 Investigational Study Drug and Disposable Device Components

Lyophilized lucinactant and disposable device components (eg, syringes, cartridges) will be shipped either to the investigational clinical study site pharmacy or to a designated location at the clinical study site. Study sites must verify each shipment via the study IRT, and report study drug shipping temperatures to Windtree as outlined in the study manual.

6.9.2 Ancillary Supplies

Ancillary supplies (eg, nCPAP system, nasal prongs) will be shipped either to the investigational clinical study site NICU or to a designated location at the clinical study site. Study sites must verify each shipment to Windtree via the Clinical Supply Receipt Form that accompanies the shipment.

6.9.3 Dispensing

Study supplies (study drug, cartridges, related study equipment) will be dispensed in accordance with the subject's randomized treatment group (Section 6.5). The NICU pharmacist or designated study personnel will provide on-site storage, dispensing, reconciliation, and documentation of study supplies as outlined in the study manual. Study drug and device disposables must be fully reconciled at the end of the study. The unblinded study clinical site monitor will provide oversight

of these tasks and communicate any significant findings or indications of noncompliance to Windtree.

6.9.4 Storage of Lucinactant and AEROSURF Delivery System

Lyophilized lucinactant must be stored in a secured area of the hospital pharmacy or NICU at 2°C to 8°C and protected from light until use. The refrigerated storage should have an alarm for out of range temperatures. Study sites must monitor and log storage temperatures daily. All temperature excursions should be reported to Windtree as outlined in the study manual (see also Section 9.2).

The ADS will be delivered separately and must also be stored in a secure location under the recommended storage conditions outlined in the ADS Operator's Manual.

6.10 Study Compliance

Study compliance to treatment administration will be based on the timing and duration of actual study treatment delivered in comparison to the expected timing and duration based on the study treatment to which each subject was randomized. Aerosolization time and duration will be tracked by the ADS, which will display a continual count of lucinactant exposure time throughout the aerosol delivery period. Duration of sham treatment will be 110 minutes for the initial treatment and 50 minutes for repeat treatments. The duration of lucinactant exposure or sham treatment will be documented in the study eCRF.

The number of subjects randomized but not treated, and the number of subjects whose study treatment is discontinued early will be recorded in the eCRF and summarized in the study report.

6.11 Study Drug and Device Accountability

It is the responsibility of the PI and designee to ensure that all study supplies (vials of lucinactant for inhalation, all components of the ADS, related equipment) are inventoried and appropriately stored in accordance with study guidance documents (eg, study protocol, ADS Operator's Manual, study manual), and used only for study subjects, by trained staff.

6.11.1 Study Supply Accountability

The following guidelines must be followed to ensure the storage and accountability of the study supplies is consistent with the study protocol:

1. Used or partially used vials of lucinactant for inhalation and disposable device components must be kept separate from unused supplies throughout the life of the study.

2. Designated study personnel will return all unused study drug vials to the pharmacy or the clinical supply storage area immediately after the completion of study treatment.
3. Reconciliation of study supplies will be performed at each study visit by the unblinded clinical site monitor and recorded appropriately in the pharmacy log and drug and device accountability records. Following reconciliation, study supplies will be destroyed and/or returned.
4. Storage conditions, as described in the study manual, will be assessed and documented by the unblinded clinical site monitor at each study visit (ensuring all supplies are kept in a secure area with restricted access).
5. Dispensing information must be recorded on the inventory log and kept with the study site records in the pharmacy binder throughout the study.
6. Study sites will not dispense the study supplies to any personnel other than those listed on Form FDA 1572 - Statement of Investigator, or on the Signature and Delegation Log.

7 DATA MONITORING COMMITTEE

The purpose of the data monitoring committee (DMC) is to evaluate the degree of risk involved in study subject participation within each treatment group and to determine if study continuation in accordance with the current protocol holds the potential to institute any undue harm or threat to the safety and welfare of study subjects. During the primary phase (screening to 36 weeks PMA), the chair of the DMC will receive regular reports on SAEs and AEs of interest (see Section 9.1) and DMC members will be updated on the program and trial status twice a year (outside of formal meetings) at spring and winter neonatology national meetings. In addition, there will be one planned meeting during study conduct, when enrollment is approximately 1/3 of the total enrollment of 70 (ie, approximately 28 subjects). An ad hoc meeting of the DMC will occur if the chair deems it necessary to address safety in the study. The DMC may recommend that study enrollment be suspended if safety concerns are identified or suspected.

The DMC will also convene meetings after all subjects have completed 36 weeks PMA and 12 months follow-up.

The DMC will consist of 3 to 5 experts in the field of RDS; at least 2 of the experts must be neonatologists.

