The administration of study treatment may be discontinued at any time prior to the completion of dosing if certain device malfunctions or interruptions occur which cannot be corrected in a safe and timely manner or based on the clinical judgment of the PI. Reasons for discontinuation of study treatment include, but are not limited to the following:

1. A device malfunction occurs
2. The device shuts down as a result of a detected out of range condition
3. An AE or ADE which places subject at risk occurs (eg, pulmonary hemorrhage; airway obstruction)
4. If, in the PI's best medical judgment, initiating or continuing the subject's exposure to study treatment is not in the best interest of the subject's safety
5. Signs of acute respiratory deterioration develop, as evidenced by a clinically significant increase in respiratory rate or effort (work of breathing) plus at least one of the following:
 - a) A persistent (at least 10 minutes) $\text{FiO}_2 \geq 0.70$ or sustained increase from baseline by ≥ 0.30 to maintain SpO_2 90% to 95%
 - b) A persistent (at least 5 minutes) transcutaneous $\text{PCO}_2 > 70 \text{ mmHg}$ or an increase from baseline by $\geq 20 \text{ mmHg}$
 - c) Recurring episodes of bradycardia
 - d) A sustained apneic event (≥ 20 seconds)

Subjects whose treatment is discontinued based on the PI's judgment will continue in the study. Subjects whose treatment is discontinued based on the parent/guardian's withdrawal of consent will be withdrawn from the study and no further data collection will be done.

Statistical Analysis The statistical analysis of objectives will be based on all enrolled preterm neonates. The subjects enrolled open-label with active treatment (the first 2 subjects from each site) will be summarized separately; however, AEs and other safety information may also be pooled with data from the double-blind portion of the study.

For the efficacy analysis, populations of all randomized subjects who received any treatment (modified intent-to-treat [mITT]) and subjects with no major protocol deviations or treatment interruptions (per-protocol) will be evaluated, based upon the treatment group to which they were randomized. For the safety analysis, all subjects randomized to the control group or who received any lucinactant for inhalation (including partial doses) will be evaluated, based upon the treatment they actually received.

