3.2 Dose and Device Description and Rationale

In this study, approximately 65 subjects will be randomized to active treatment and will receive aerosolized lucinactant through the ADS in conjunction with nCPAP. Approximately 65 subjects will be randomized to the control group and will receive nCPAP alone with “sham” study drug treatment.

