5 STUDY POPULATION SELECTION

5.1 Study Population

This study population will be comprised of preterm neonates $26^{0/7}$ to $32^{6/7}$ completed weeks PMA who are receiving care in a NICU and are receiving nCPAP as the primary support modality for RDS. This study is anticipated to enroll approximately 130 preterm neonates (approximately 50% in each treatment group) who are candidates for SRT and nCPAP. Subjects will be enrolled by strata: subjects $26^{0/7}$ to $28^{6/7}$ completed weeks PMA and subjects $29^{0/7}$ to $32^{6/7}$ completed weeks PMA.

The study population will be randomized in a 1:1 ratio into 1 of 2 treatment groups (see Section 6.4).

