13 STATISTICAL METHODS AND DETERMINATION OF SAMPLE SIZE

It is anticipated that up to 130 subjects (approximately 50% in each treatment group) will be enrolled into the study.

A complete outline of the all planned analyses for the study, including the handling of missing data, is provided in the Statistical Analysis Plan for this protocol.

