13.2 Statistical and Analytical Plans

The statistical analysis of both the primary and secondary objectives will be based on all enrolled preterm neonates who received study therapy. The first 2 subjects at each site, which were treated with open-label active therapy will be summarized separately. However, the safety data from these subjects may be pooled with the safety data from the subjects that received blinded therapy. The efficacy data will not be pooled.

For the efficacy analysis, all randomized subjects who received study therapy (modified intent-to-treat [mITT]) and subjects with no major protocol deviations (per-protocol) will be evaluated, based upon the treatment group to which they were randomized. If necessary, a population of subjects without treatment interruptions will also be defined and analyzed. For the safety analysis, all control subjects and subjects who received any amount of aerosolized lucinactant will be evaluated, based upon the treatment they actually received. All analyses will be performed for all subjects combined by treatment group and by gestational age strata.

All continuous variables (eg, weight, body temperature) will be summarized using number (n), mean, standard deviation (SD), median, 1st quartile, 3rd quartile, minimum, and maximum. All discrete variables (eg, sex, AEs, common complications of prematurity), will be summarized using frequency (n) and percent. Sites will be pooled for statistical analyses by geographic region.

The primary endpoint (the incidence of respiratory failure due to RDS or death within 28 days of life) is defined in Section 4.3.1. Respiratory failure due to RDS is defined as intubation (including intratracheal catheter placement) for MV and/or surfactant administration and will be compared between active treatment and control using the Cochran-Mantel-Haenszel (CMH) test, controlling for pooled sites.

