13.4 Sample Size and Randomization

A total of up to 130 study subjects (approximately 50% in each treatment group) will be enrolled.

Given that this is an estimation study, it is not powered to achieve statistical significance; however, based on the results from previous studies, it will be sufficient to show a qualitative improvement for the active group.

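### The planned DMC count of 28 is one third of neither 70 nor 130, the open-label infants have no stated place in the 130, and the SAP lets them into an efficacy difference from which Protocol 13.2 keeps them out

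*Protocol*

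**What the plan says.** **DMC meeting.** Protocol 7, repeated in 13.3, places the single planned in-study meeting "when enrollment is approximately 1/3 of the total enrollment of 70 (ie, approximately 28 subjects"). The Protocol synopsis (Interim Analyses) and the SAP executive summary give only the fraction, one third or 33%, with no count.

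**Total.** Protocol 13.4: "A total of up to 130 study subjects (approximately 50% in each treatment group) will be enrolled". Section 13 says the same, and section 5.1 has "This study is anticipated to enroll approximately 130 preterm neonates (approximately 50% in each treatment group"). Section 3.2 adds that "approximately 65 subjects will be randomized to active treatment", with a like number randomised to control. Section 5.1 sets 1:1 randomisation. The synopsis also sets a minimum of 7 infants per arm in each gestational-age stratum and labels it about 20% of the total.

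**Open-label infants.** The first two at every site receive active treatment unmasked. Protocol 6.5 passes them through the same central allocation system, "including the open-label subjects (the first 2 subjects at each site"). The synopsis foresees about 20 sites, SAP 2.1 about 10.

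**Analysis.** Protocol 13.2: "The first 2 subjects at each site, which were treated with open-label active therapy will be summarized separately". It allows their safety data to be pooled but rules out pooling their efficacy data. SAP 4.1 takes the opposite line: these infants get no separate summary, and efficacy rests on all enrolled neonates, called the ITT population. SAP 4.2 then computes the active-minus-control difference (delta).

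**The concern.** The parenthetical count does not follow from its stated base, and that base is not the Protocol's total. A site or committee member could derive 23, 28 or 43 as the trigger for the same meeting.

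The enrolment ceiling has a similar gap. Two randomised arms of 65 leave no room in 130 for 20 to 40 further infants, and words such as approximately and up to cannot absorb that many.

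The more consequential matter is who enters the efficacy comparison. The open-label infants are all on active treatment, are treated unmasked, and have no concurrent randomised control. Intubation, the core of the primary endpoint, is decided by clinicians. Adding such infants to one arm weakens both the randomisation and the masking behind the difference. SAP 4.2 says the difference may help plan later studies and support efficacy, and SAP 1.2 says the estimate will feed future sample-size calculations.

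**Working it through.** **1. DMC count**

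Inputs: fraction 1/3, base 70, count 28 (Protocol 7, 13.3); total 130 (Protocol 5.1, 13, 13.4).

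- Stated base: 70/3 = 23.3, and 28/70 = 40.0%. The stated 28 is not reproduced.
- Protocol total: 130/3 = 43.3, and 28/130 = 21.5%. Not reproduced.
- Total for which 28 is exactly one third: 28 × 3 = 84, stated nowhere.
- Nearest base that can be built from stated figures: 35 + 35 (SAP executive summary) + 2 × 10 sites = 90, and 90/3 = 30. The SAP's 720 screened at 8:1 also gives 720/8 = 90. This hints at a smaller design with open-label infants counted on top. It is an inference only, since the text itself names 70.

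**2. Enrolment ceiling**

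Inputs: 65 + 65 = 130 randomised (Protocol 3.2); 2 open-label infants per site, so 2 × 20 = 40 (Protocol sites) or 2 × 10 = 20 (SAP sites). Figures for 10 sites are in brackets.

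| Where open-label infants are counted | Enrolled | Randomised, active v control | Active share of enrolled | What fails |
|---|---|---|---|---|
| On top of 130 | 130 + 40 = 170 (150) | 65 v 65 | 105/170 = 61.8% (85/150 = 56.7%) | the 130 ceiling; the even split |
| Inside 130, equal randomised arms | 130 | (130 − 40)/2 = 45 v 45 (55 v 55) | 85/130 = 65.4% (75/130 = 57.7%) | 65 randomised per arm; the even split |
| Inside the active 65 | 130 | 65 − 40 = 25 v 65 (45 v 65) | 65/130 = 50% | 1:1 randomisation |

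Each reading breaks at least one stated feature.

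Stratum label: 2 × 7 = 14. 14/70 = 20%, but 14/130 = 10.8%. The label fits 70, not 130.

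**3. Who enters the delta**

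- Protocol 13.2: open-label infants summarised apart; efficacy data not pooled. The synopsis also has them summarised separately.
- SAP executive summary (Analysis Populations): because of early termination, all enrolled treated neonates form the only population. The no-pooling rule is not mentioned.
- SAP 1.2.1: ITT means all randomised subjects.
- SAP 2.2.1: 1:1 assignment follows the two open-label infants at each site.
- SAP 4.1: efficacy on all enrolled, labelled ITT, with no separate open-label summary.
- SAP 4.2: delta calculated for the primary and secondary efficacy endpoints.

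Read together, 4.1 and 4.2 put the open-label infants in the active arm of the delta. SAP 1.2.1 would exclude them only if they do not count as randomised, which the documents leave unclear.

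Possible share: 12 infants were enrolled, and the number of enrolling sites is not given. Assuming that each enrolling site supplied its two open-label infants, they would be 2 of 12 at one site, 6 of 12 at three sites and all 12 at six.

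**The case against.** Several points count on the other side.

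- **The DMC rule is consistent in its fraction.** All four statements say one third; only the base and the count are wrong. The meeting was a safety review with no efficacy boundary and no alpha spent. The chair received regular reports, ad hoc meetings were possible, and the planned meeting was cancelled when enrolment stopped at 12. This stands. A reader might infer a loss of safety oversight or an affected error rate, and the documents support neither.
- **The even split need not fail.** A reader might infer that 50:50 is impossible however the open-label infants are counted. The third row of the table shows otherwise. That reading has textual support: the open-label rule is a note to the table giving about 65 per arm, the infants pass through the same allocation system, and the synopsis groups open-label and masked infants as randomised to lucinactant. Its cost is 1:1 randomisation.
- **The SAP gives a reason for one population.** Early termination explains a single analysis set, and the Protocol too begins from all enrolled neonates. But the Protocol then separates the open-label infants, and the SAP reverses that without saying why.
- **Pooling is not beyond doubt.** A reader might infer that the open-label infants certainly enter the delta. The ITT definition in SAP 1.2.1 leaves room for excluding them, so the firm statement is that SAP 4.1 and 4.2 as written include them and that the SAP disagrees with itself.
- **Other SAP mismatches are clerical.** The site count, the screening projection and the differing arm sizes (35/35, 35/80, 65/65) drive no analysis.

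**Conclusion.** The point holds in three parts of unequal weight.

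First, the DMC count is wrong on either base: 28 against 23 (base 70) or 43 (base 130). It matters only for the record and for reuse of the design.

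Second, the enrolment figures cannot all be true together, by 40 infants at 20 sites or 20 at 10 sites. Which figure gives way depends on a counting rule that the documents never state. The study was not powered for significance, so no power claim is affected.

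Third, the SAP departs from Protocol 13.2 on open-label efficacy data without recording it as a change, and this alone can alter a reported number. How far is unknown, because the documents do not say how many of the 12 infants were open-label. The range shown above rests on the assumption of two per enrolling site. With no testing planned, the harm lies in a descriptive difference that later planning may rely on.

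**What to change.** - **Protocol 7 and 13.3:** name the base and derive the count from it: about 43 if the base is 130, 150/3 = 50 or 170/3 = 57 if open-label infants are on top. If 28 is intended, state its true fraction, about 22% of 130.
- **Protocol 1.1, 5.1, 13 and 13.4:** state randomised and open-label numbers separately, and say to which the 50% applies. Reconcile the stratum minimum and its percentage with the chosen total.
- **SAP 4.1, 4.2 and 1.2.1:** use one ITT definition. Base the delta on the masked randomised infants and show open-label efficacy in its own column; or record the pooling as a deliberate departure from Protocol 13.2 and give the delta with and without these infants.
- **SAP executive summary, 2.1 and 2.2.1:** align arm sizes, sites and screening figures if the text is reissued.

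The cost is text edits and one extra table column. The real downside is that fewer of the 12 infants remain in the randomised comparison. In a reused design, a count above 28 would move the planned meeting later, with the chair's regular reports and ad hoc meetings still in place.
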